10.5.3.3. Reporting Adverse Events

The Sponsor (or the delegates) must be informed about an SAE within 24 hours of the site knowing about the event. The Investigator must promptly forward to the Sponsor (or the delegates) a duly completed Investigator SAE Report Form for Development Drug provided by the company, even if the data are incomplete or if it is obvious that more data will be needed to make any conclusions.

Additional information (e.g. autopsy or lab reports) should be provided to the Sponsor in a timely fashion to ensure accurate follow-up of each case.

The Sponsor (or the delegates) will communicate safety information and Suspected Unexpected Serious Adverse Reactions – SUSARs) to the appropriate agency (ies) and all active Investigators, in accordance with applicable regulatory requirements. The appropriate IRB/IEC will also be informed by the Investigator or the Sponsor, as specified by the applicable regulatory requirements in the Korea Food and Drug Administration (KFDA) or the appropriate agency (ies). Investigators are to retain evidence of such IRB/IEC notification in their study binder.

A copy of the Investigator SAE report form and the completion guide will be provided to the Investigator.

If known by the Investigator, Serious Adverse Events up to 30 days after the final study visit must be reported to the Sponsor, even if the Investigator is certain that they are in no way associated with the study drug.

Adverse Events that the Investigator thinks may be associated with the study medication must be reported to the Sponsor regardless of the time between the event and the end of the study.

Follow-Up Procedures for Serious Adverse Events

The Sponsor shall promptly investigate all safety information received by it. Follow-up information to a safety report shall be submitted as soon as the relevant information is available.

Relevant information such as discharge summaries, autopsy reports, and medical consultations shall be reviewed in detail by the Investigator. The Investigator shall comment on any event, abnormal laboratory result, or any other finding, noting whether it shall be considered a serious or nonserious AE or considered part of the subject's history. In addition, the Investigator shall report on an SAE form all subsequent events or other findings determined to be relevant and shall state for each event or finding whether it is related to study drug. All events determined to be nonserious shall be reported on the relevant eCRF page.

10.5.3.4. Clinical Laboratory Determinations

Samples for hematology and biochemistry assessments will be collected at every visit and the assessments will be conducted at the central laboratory or local laboratory. At Screening (Visit 1), the Investigator will assess the clinical significance of any values outside the reference ranges provided by the central laboratory; subjects with abnormalities judged to be clinically significant will be excluded from the study.

However, blood test for hemoglobin and hematocrit level can be conducted by the central laboratory. Biweekly basis data for hemoglobin and hematocrit level should be recorded on eCRF until the end of the Maintenance Phase.

HIV test will be conducted at Screening Visit (Visit 1), and CRP, PTH and iron state (Fe, ferritin, transferritin saturation) will be tested at Screening Visit (Visit 1), Baseline Visit (Visit 4), Week 12 (Visit 7), Week 28/Withdrawal (Visit 11), Week 40 (Visit 14) and Week 52/Withdrawal (Visit 17).

Hematology: Hb, Hct, RBC, WBC, Plt, WBC diff count, PT/PTT

Serum biochemistry: Na, K, Cl, total CO₂, Ca, P, ALT/AST, Alkaline phosphatase, Total bilirubin, Glucose, Albumin, Total cholesterol, BUN, Serum creatinine, Uric acid

Iron evaluation: Fe, ferritin, transferritin saturation

* Vitamin B12 and Folate evaluation will be conducted at Screening Visit (Visit 1).

10.5.3.5. Vital Signs

Vital sign measurements will be documented at every visit before administration of study medication. The parameters will include sitting pulse rate and sitting systolic and diastolic blood pressure. Pulse rate and blood pressure readings will be taken after the subject has been sitting for 5 minutes; the same arm should be consistently used for the measurements. Subjects found to have abnormal blood pressure will be evaluated by the PI to ensure to determine if they are eligible to continue in the study.

- Pulse
- Systolic/diastolic blood pressure

10.5.3.6. Chest X-rays

A plain postero-anterior chest X-ray should be taken unless a chest X-ray was performed and was clear within 3 months prior to Screening visit. The chest X-ray should be taken at Screening Visit (Visit 1), Baseline Visit (Visit 4), Week 28/Withdrawal (Visit 11) and Week 52 (Visit 17). However, chest X-ray result performed within 6 weeks prior to Baseline Visit can be used for baseline result.

10.5.3.7. Physical Examination

Physical examinations will be performed at every visit. The physical examination will include an examination of general appearance; eyes; ears; nose; throat; and the abdominal, skin/mucosa, lymphatic, cardiovascular, respiratory, neurological, and musculoskeletal systems.

10.5.3.8. Weight and Height

Weight (measured in kilograms) is measured at every visit and height (measured in centimeters), at the Screening Visit.

10.5.3.9. Pregnancy Test

For female subjects of childbearing potential, the Screening Visit (Visit 1), the Baseline Visit (Visit 4), Week 28/Withdrawal Visit (Visit 11) and Week 52/Withdrawal Visit (Visit 17) serum β -hCG pregnancy test results must be negative.

10.5.3.10. Concomitant medications

Should any treatment other than the investigational product be taken by the subject at screening or at any time during the course of the study (including over-the-counter products and nutraceuticals), an accurate record must be kept in the clinic chart (source documentation) and eCRF. This record should include the name of the drug, the daily dose, the route and date(s) of administration, and the indication for use.

10.5.4. Immunological Assessment**10.5.4.1. Anti-epoetin antibody****1) Time of Blood Sampling**

The blood sampling to measure anti-epoetin antibodies will be conducted at Screening Visit (Visit 1), Baseline Visit (Visit 4), Week 28/Withdrawal Visit (Visit 11), and Week 52/Withdrawal Visit (Visit 17).

2) Measured Variables

Blood samples for the determination of anti-epoetin antibodies will be sent from the site to the central antibody concentration analysis center for the clinical laboratory test.

10.5.5. Schedule of Procedures/Assessments

10.5.5.1. Schedule of Procedures/Assessments

Protocol Activity	Titration Phase						4	Maintenance Phase												11	Open-Label Extension Phase							
	1	1a	2	2a	3	3a		4a	5	5a	6	6a	7	7a	8	8a	9	9a	10		10a	12	13	14	15	16	17	
Visit Number ⁸⁾	1	1a	2	2a	3	3a	4	4a	5	5a	6	6a	7	7a	8	8a	9	9a	10	10a	11	12	13	14	15	16	17	
Week Number	-12 Screening	-10	-8	-6	-4	-2	0 Baseline	2	4	6	8	10	12	14	16	18	20	22	24	26	28/W ⁷⁾	32	36	40	44	48	52/W ⁷⁾	
Informed Consent ¹⁾	X																											
Inclusion/Exclusion Criteria	X						X																					
Demographic Information	X																											
Medical and Surgical History	X																											
Prior Medication History	X																											
Anemia of Chronic Renal Failure History	X																											
Physical Examination	X		X		X		X		X		X		X		X		X		X		X	X	X	X	X	X	X	X
Vital Signs	X		X		X		X		X		X		X		X		X		X		X	X	X	X	X	X	X	X
Weight	X		X		X		X		X		X		X		X		X		X		X	X	X	X	X	X	X	X
Height	X																											
Hematology/Biochem ²⁾	X		X		X		X		X		X		X		X		X		X		X	X	X	X	X	X	X	X
Hb/Hct ²⁾		X		X		X		X		X		X		X		X		X		X								
CRP	X						X						X								X			X				X
Iron evaluation and PTH ²⁾	X						X						X								X			X				X
Vitamin B12 and Folate	X																											

Protocol Activity	Titration Phase						4	Maintenance Phase												11	Open-Label Extension Phase							
	1	1a	2	2a	3	3a		4a	5	5a	6	6a	7	7a	8	8a	9	9a	10		10a	12	13	14	15	16	17	
Visit Number ⁸⁾	-12 Screening	-10	-8	-6	-4	-2	0 Baseline	2	4	6	8	10	12	14	16	18	20	22	24	26	28/W ⁷⁾	32	36	40	44	48	52/W ⁷⁾	
HIV Serum Testing	X																											
Chest X-ray ³⁾	X						X														X						X	
Anti-Epoetin Antibodies ⁴⁾	X						X														X						X	
Pregnancy Testing ⁵⁾	X						X														X						X	
Concomitant Medication	X		X		X		X		X		X		X		X		X		X		X	X	X	X	X	X	X	
Adverse Events			X		X		X		X		X		X		X		X		X		X	X	X	X	X	X	X	
PDA10 or Eprex [®] Administration ⁶⁾	X		X		X		X		X		X		X		X		X		X		X	X	X	X	X	X		
Assessment of compliance			X		X		X		X		X		X		X		X		X		X	X	X	X	X	X	X	

* W = withdrawal visit

- 1) If the subject is unable to provide written informed consent, written consent must be obtained from the subject's representative and verbal assent must be obtained from the subject.
- 2) If the laboratory values above exceed the upper limit of reference range, the re-test will be conducted by the investigator one more time to exclude the cases where the laboratory values continuously exceed the upper limit of reference range. Hemoglobin level and hematocrit level checked by the central laboratory will be recorded on a biweekly basis on eCRF until the end of the Maintenance Phase. Increases in dose should not be made more frequently than once 4 weeks. The clinical laboratory test, except hemoglobin and hematocrit will be conducted once four weeks.
- 3) Chest X-ray result within 3 months prior to Screening Visit will be available for screening. In addition, chest X-ray result performed within 6 weeks prior to Baseline Visit can be used for baseline result.
- 4) The blood sampling to measure anti-epoetin antibodies will be conducted at Screening Visit (Visit 1), Baseline Visit (Visit 4), Week 28/ Withdrawal Visit, and Week 52/ Withdrawal Visit.
- 5) Serum pregnancy test at Screening Visit, Baseline Visit, Week 28/ Withdrawal Visit and Week 52/Withdrawal Visit will be conducted.
- 6) Subjects will be administered Eprex[®] for the titration phase, PDA10 or Eprex[®] for the maintenance phase, and PDA10 for the open-label extension phase.

- 7) If subjects are withdrawn during the maintenance phase and open-label extension phase, the same procedure will be conducted with Visit 11 and Visit 17, respectively.
- 8) Visit window is ± 5 days. However, V4 blood sampling is allowed at -7 days from planned V4 date.

10.5.5.2. Description of Procedures/Assessments Schedule

Titration Phase

Visit 1 (Screening, Week -12)

Prior to any study activities, subjects will be asked to read and sign an informed consent form that has been approved by an IRB. Subjects will be given adequate time to consider any information concerning the study, given to them by the Investigator or designee.

Following assessments at this visit include:

- Signing informed consent form: The subject is given the oral explanation and written summarized exploratory statement about the study objectives, method, limitations and risks, study duration, etc. The subject signs and dates the consent form. One copy of the signed consent form is given to the subject.
- Confirm inclusion/exclusion criteria
- Demographic information
- Anemia of chronic renal failure history
- Significant past medical history (including allergies), concomitant disease, and drug history and concomitant drugs
- Vital signs (pulse and systolic and diastolic BP)
- Height and weight
- Blood sample for clinical laboratory values (Hematology/Serum biochemistry, CRP, PTH, Iron evaluation, Vitamin B12 and Folate, HIV, Anti-erythropoietin antibody, Serum pregnancy test)
- Physical examination
- Chest X-ray

Only patients who meet all inclusion/exclusion will be allowed to continue the remaining steps and administer Eprex[®]. If not, terminate the patient from the study.

Visit 1a (Week -10)

Clinical laboratory test for Hb and Hct will be performed.

Visit 2 (Week -8)

The following procedures will be conducted at this visit:

- Physical examination
- Vital signs (pulse and systolic and diastolic BP)

- Weight
- Blood sample for clinical laboratory values (Hematology/Serum biochemistry)
- Concomitant drugs
- Adverse events
- Eprex[®] administration
- Assessment of compliance

Visit 2a (Week -6)

Clinical laboratory test for Hb and Hct will be performed.

Visit 3 (Week -4)

The following procedures will be conducted at this visit:

- Physical examination
- Vital signs (pulse and systolic and diastolic BP)
- Weight
- Blood sample for clinical laboratory values (Hematology/Serum biochemistry)
- Concomitant drugs
- Adverse events
- Eprex[®] administration
- Assessment of compliance

Note: The duration of the titration phase is 12 weeks, and a prolongation of the titration phase will be allowed up to 20 weeks in substantiated cases. If a subject need a prolongation of the titration phase after Visit 3, the next visit will be Visit 3-1 (4 extra weeks of titration phase) and Visit 3-2 (8 extra weeks of titration phase), and the same procedures will be conducted with Visit 3.

Visit 3a (Week -2)

Clinical laboratory test for Hb and Hct will be performed.

Maintenance Phase

Visit 4 and Randomization (Baseline, Week 0)

Subjects with hemoglobin level within the target range between 10.0 and 12.0 g/dl will have the following procedures performed/recorded prior to study drug administration:

Review of inclusion/exclusion criteria

The following steps must be followed for the subjects to qualify for randomization:

- Physical examination
- Vital signs (pulse and systolic and diastolic BP)
- Weight
- Blood sample for clinical laboratory values (Hematology/Serum biochemistry, CRP, PTH, Iron evaluation, Anti-erythropoietin antibody, Serum pregnancy test)
- Chest X-ray (the result performed within 6 weeks prior to Baseline Visit can be used)
- Concomitant drugs
- Adverse events
- PDA10 or Epnex[®] administration (**Post randomization**)
- Assessment of compliance

Visit 4a (Week 2)

Clinical laboratory test for Hb and Hct will be performed.

Visit 5 (Week 4)

The following procedures will be conducted at this visit:

- Physical examination
- Vital signs (pulse and systolic and diastolic BP)
- Weight
- Blood sample for clinical laboratory values (Hematology/Serum biochemistry)
- Concomitant drugs
- Adverse events
- PDA10 or Epnex[®] administration
- Assessment of compliance

Visit 5a (Week 6)

Clinical laboratory test for Hb and Hct will be performed.

Visit 6 (Week 8)

The following procedures will be conducted at this visit:

- Physical examination
- Vital signs (pulse and systolic and diastolic BP)
- Weight
- Blood sample for clinical laboratory values (Hematology/Serum biochemistry)
- Concomitant drugs
- Adverse events
- PDA10 or Eprex[®] administration
- Assessment of compliance

Visit 6a (Week 10)

Clinical laboratory test for Hb and Hct will be performed.

Visit 7 (Week 12)

The following procedures will be conducted at this visit:

- Physical examination
- Vital signs (pulse and systolic and diastolic BP)
- Weight
- Blood sample for clinical laboratory values (Hematology/Serum biochemistry, CRP, PTH, Iron evaluation)
- Concomitant drugs
- Adverse events
- PDA10 or Eprex[®] administration
- Assessment of compliance

Visit 7a (Week 14)

Clinical laboratory test for Hb and Hct will be performed.

Visit 8 (Week 16)

The following procedures will be conducted at this visit:

- Physical examination
- Vital signs (pulse and systolic and diastolic BP)
- Weight
- Blood sample for clinical laboratory values (Hematology/Serum biochemistry)
- Concomitant drugs
- Adverse events
- PDA10 or Eprex[®] administration
- Assessment of compliance

Visit 8a (Week 18)

Clinical laboratory test for Hb and Hct will be performed.

Visit 9 (Week 20)

The following procedures will be conducted at this visit:

- Physical examination
- Vital signs (pulse and systolic and diastolic BP)
- Weight
- Blood sample for clinical laboratory values (Hematology/Serum biochemistry)
- Concomitant drugs
- Adverse events
- PDA10 or Eprex[®] administration
- Assessment of compliance

Visit 9a (Week 22)

Clinical laboratory test for Hb and Hct will be performed.

Visit 10 (Week 24)

The following procedures will be conducted at this visit:

- Physical examination
- Vital signs (pulse and systolic and diastolic BP)
- Weight
- Blood sample for clinical laboratory values (Hematology/Serum biochemistry)
- Concomitant drugs
- Adverse events
- PDA10 or Eprex[®] administration
- Assessment of compliance

Visit 10a (Week 26)

Clinical laboratory test for Hb and Hct will be performed.

Visit 11 (Week 28/Withdrawal)

The following procedures will be conducted at this visit:

- Physical examination
- Vital signs (pulse and systolic and diastolic BP)
- Weight
- Blood sample for clinical laboratory values (Hematology/Serum biochemistry, CRP, PTH, Iron evaluation, Anti-erythropoietin antibody, Serum pregnancy test)
- Chest X-ray
- Concomitant drugs
- Adverse events
- PDA10 administration (subjects who participate in the OLE phase only)
- Assessment of compliance

* Visit 11 at Week 28 will serve as the entry visit for the open label extension phase.

Subjects who signed the ICF will perform the next visit.

Subject who will NOT be participated in the extension phase will be returned to the standard treatment provided at the hospital/clinic respectively.

Visit 12 (Week 32)

The following procedures will be conducted at this visit:

- Physical examination
- Vital signs (pulse and systolic and diastolic BP)
- Weight
- Blood sample for clinical laboratory values (Hematology/Serum biochemistry)
- Concomitant drugs
- Adverse events
- PDA10 administration
- Assessment of compliance

Visit 13 (Week 36)

The following procedures will be conducted at this visit:

- Physical examination
- Vital signs (pulse and systolic and diastolic BP)
- Weight
- Blood sample for clinical laboratory values (Hematology/Serum biochemistry)
- Concomitant drugs
- Adverse events
- PDA10 administration
- Assessment of compliance

Visit 14 (Week 40)

The following procedures will be conducted at this visit:

- Physical examination
- Vital signs (pulse and systolic and diastolic BP)
- Weight
- Blood sample for clinical laboratory values (Hematology/Serum biochemistry, CRP, PTH, Iron evaluation)

- Concomitant drugs
- Adverse events
- PDA10 administration
- Assessment of compliance

Visit 15 (Week 44)

The following procedures will be conducted at this visit:

- Physical examination
- Vital signs (pulse and systolic and diastolic BP)
- Weight
- Blood sample for clinical laboratory values (Hematology/Serum biochemistry)
- Concomitant drugs
- Adverse events
- PDA10 administration
- Assessment of compliance

Visit 16 (Week 48)

The following procedures will be conducted at this visit:

- Physical examination
- Vital signs (pulse and systolic and diastolic BP)
- Weight
- Blood sample for clinical laboratory values (Hematology/Serum biochemistry)
- Concomitant drugs
- Adverse events
- PDA10 administration
- Assessment of compliance

Visit 17/Withdrawal (Week 52)

The following procedures will be conducted at this visit:

- Physical examination
- Vital signs (pulse and systolic and diastolic BP)
- Weight
- Blood sample for clinical laboratory values (Hematology/Serum biochemistry, CRP, PTH, Iron evaluation, Anti-erythropoietin antibody, Serum pregnancy test)
- Chest X-ray
- Concomitant drugs
- Adverse events
- Assessment of compliance

Unscheduled Visit

With regard to adverse events, change in concomitant drugs, withdrawals and the cases requiring medical treatment as a result of the clinical tests, if the subject visits on the day which is not scheduled, the corresponding matters should be recorded in the relative form. The visit schedule should not be changed due to the unscheduled visit.

Subject Completion

Subjects will be asked to participate in the open-label extension (OLE) phase at Visit 1. Among them, subjects who complete the Week 28 will be offered PDA10 treatment.

After end of open-label extension phase, subject to return to the standard treatment provided at the hospital/clinic respectively.

Handling of Biological Samples

Central laboratory will provide with a laboratory manual which will explain detailed descriptions of collection, preparation and labeling/shipping requirements for biological samples to each site.

10.6. STATISTICAL METHODS

10.6.1. General Principles of the Result Analysis

Statistical analyses will be performed using the data analysis software SAS® Version 9.2 or higher.

Statistical testing will be done at alpha=0.05 level, two-sided, without any adjustment for multiple comparisons unless otherwise specified. The p-values will be rounded to 4 decimal places; p-values less than 0.0001 will be presented as “<.0001” in all tables.

Summaries of categorical variables (nominal or ordinal) will include frequency and percentage of patients at each level of response. Continuous variable summaries will include n, mean, median, standard deviation, minimum and maximum values.

The primary efficacy analysis will be based on the PP population.

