10.6.2. Study Populations

10.6.2.1. Safety Population

The Safety Population consists of all patients who started therapy with randomized study medication.

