10.6.2.2. Full Analysis Set (FAS) Population

The Full Analysis Set (FAS) Population consists of all patients who were treated more than 4 weeks with randomized study medication and had at least one postbaseline value of the primary endpoints.

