10.6.2.3. Per-Protocol Population

The Per-Protocol Population, a subset of the FAS Population, is defined as all patients who completed the maintenance phase without any major protocol violations. The precise reasons for excluding patients from the Per-Protocol Population will be fully defined and documented before unblinding.

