10.6.3. Demographics and Clinical History Data

Demographic variables and other baseline characteristics will be summarized by treatment group for the FAS Populations. Summaries of categorical variables (nominal or ordinal) will include frequency and percentage of patients at each level of response.

For continuous variables, the number of observations, mean, median, standard deviation, minimum, and maximum will be presented.

Treatment difference will be analyzed using two sample t-test or Wilcoxon rank-sum test for continuous parameters, and using χ^2 -test or Fisher's exact test for categorical parameters.

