10.6.8. Handling of Dropouts of Missing Data

- Efficacy analysis:

Any missing data due to subject withdrawal during the study is imputed using the LOCF method. Baseline data is not carried forward to impute the missing data.

- Safety analysis:

Safety analysis is performed on observed value only.

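### Equivalence is decided on per-protocol completers alone, and the FAS meant to stand beside that set is itself selected on treatment received after randomisation

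*Protocol*

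**What the plan says.** - **Decision set.** Section 10.6.1: "The primary efficacy analysis will be based on the PP population". Section 10.6.4.1 sets the success rule: hemoglobin first, then weekly dose, each within its margin. It names no other population.
- **PP.** Under section 10.6.2.3 it is a subset of the FAS and "is defined as all patients who completed the maintenance phase without any major protocol violations". The precise reasons for exclusion are to be fixed and documented before unblinding.
- **FAS.** Under section 10.6.2.2 it is "all patients who were treated more than 4 weeks with randomized study medication and had at least one postbaseline value of the primary endpoints". Its one named use is in section 10.6.3: "Demographic variables and other baseline characteristics will be summarized by treatment group for the FAS Populations".
- **Safety Population.** Section 10.6.2.1 has no duration condition: "The Safety Population consists of all patients who started therapy with randomized study medication".
- **Missing efficacy data.** Section 10.6.8: "Any missing data due to subject withdrawal during the study is imputed using the LOCF method". Baseline values are not carried forward.
- **Ways of leaving PP.** Section 10.3.4 lists adverse events and lack of efficacy among the reasons for discontinuation. Section 10.4.5 ends participation for any patient whose code is broken at the site.
- **Expected loss.** Section 10.6.7.2 allows for 20% exclusion from PP: 126 evaluable and 158 enrolled per group.

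**The concern.** Completing 28 weeks is an outcome of treatment. If the two products differ in how many patients they fail, or in which ones, those patients disappear from both the hemoglobin and the dose comparison, and the remaining completers may look more alike than the arms as randomised. Section 10.2 relies on randomisation for a valid comparison, and selection by completion weakens that protection.

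The usual safeguard in an equivalence trial is a companion analysis on a set close to all randomised patients. Here the set available for it has the same kind of flaw. Hemoglobin is measured at Week 2, so a patient who stops by Week 4 can have a post-baseline value and still fall outside the FAS. An analysis plan that gave this FAS an efficacy role would inherit the gap. At stake is whether the trial's central conclusion could be reached with nothing in the protocol requiring a check against the fuller comparison.

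**Working it through.** **Who is counted**

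| Patient | Safety | FAS | PP |
|---|---|---|---|
| Stops by Week 4, with a Week 2 hemoglobin | yes | no | no |
| Stops after Week 4 (lack of efficacy, adverse event, unblinding) | yes | yes, if a post-baseline value exists | no |
| Completes with a major violation | yes | yes, if a post-baseline value exists | no |
| Completes without a major violation | yes | yes | yes |

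The withdrawal rule in section 10.6.8 therefore has almost nothing to act on in PP, the only set named for efficacy.

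**Reproducing the plan** (inputs from section 10.6.7.2: SD 1.1 g/dl and 86.6 IU/kg, margins 0.5 g/dl and 45 IU/kg, 1:1 allocation)

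- Hemoglobin: 2 × (1.645 + 1.96)² × 1.1² / 0.5² = 125.80, so 126 per group.
- Weekly dose: 2 × (1.645 + 1.96)² × 86.6² / 45² = 96.26, so 97 per group.
- Enrolment: 126 / 0.80 = 157.5, so 158 per group and 316 in all. The plan's figures reproduce. About 158 − 126 = 32 patients per group are expected to be outside PP.

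**What passes in PP.** With 126 per group, an observed hemoglobin difference of 0.2 g/dl has an upper one-sided 95% limit of 0.2 + 1.645 × 1.1 × √(2/126) = 0.2 + 0.228 = 0.43, inside 0.5.

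**What passes with everyone.** With 158 per group, the largest observed difference that still passes is 0.5 − 1.645 × 1.1 × √(2/158) = 0.5 − 0.204 = 0.296 g/dl.

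**Difference among the excluded that reverses the conclusion.** With a fraction e excluded equally per arm, the all-randomised difference is (1 − e) × (PP difference) + e × D, where D is the difference among the excluded in the same direction. Setting this equal to 0.296 and solving for D:

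| Observed PP difference (g/dl) | D, e = 20% (plan) | D, e = 30% (assumed) |
|---|---|---|
| 0 | 1.48 | 0.99 |
| 0.1 | 1.08 | 0.75 |
| 0.2 | 0.68 | 0.52 |

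For example, (0.296 − 0.8 × 0.2) / 0.2 = 0.68.

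**Cost of adding the FAS.** Power is 2Φ(margin / (SD × √(2/n)) − 1.645) − 1 at a true difference of 0.

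- Hemoglobin, n = 158: 98.3% at SD 1.1 and 92.4% at an assumed SD of 1.3.
- Weekly dose, n = 158, SD 86.6: 99.7%.
- PP, n = 126: 95.0% for hemoglobin and 98.7% for dose. The hemoglobin figure exceeds the stated 90% because the plan's formula uses 1.96 where 90% power at one-sided 0.05 would need 1.645. That is a separate matter.
- Chance that all four comparisons pass, by summing the failure probabilities: at least 1 − (0.050 + 0.013 + 0.017 + 0.003) = about 92%. For PP alone the same bound is 1 − (0.050 + 0.013) = about 94%. The FAS terms assume that all 158 contribute.

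**The case against.** Several objections have force.

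- **PP as primary is defensible.** In an equivalence trial, including non-adherent patients can pull the arms together. This stands. A reader might infer that naming PP as primary is itself the error, but the protocol's text does not support that.
- **Silence is not exclusion.** A reader might infer that the FAS has no efficacy role, or that no efficacy analysis will cover patients outside PP. The protocol does not say so. The LOCF rule sits under efficacy and makes little sense without withdrawn patients. The FAS demands a post-baseline primary endpoint value, which is pointless for a baseline table. Secondary endpoints name no population, and an analysis plan not shown may give the FAS a supportive role. What remains is that this role is unstated, that the success rule can be met on PP alone, and that the 4-week condition is written into the protocol.
- **Size.** A reader might treat the whole 20% as hidden treatment failures. The protocol describes it as drop-out and protocol violation combined, and violations need not relate to outcome. It gives no figure for a difference among excluded patients, and section 10.2 says that titration blunts hemoglobin differences. Only thresholds can be given, and from a PP difference of 0 the threshold is high.
- **A wider FAS with LOCF could flatter equivalence.** All patients receive Eprex before randomisation and dose decisions come every four weeks, so values carried forward from the first weeks largely reflect pre-randomisation treatment. This stands, and the fix has to deal with it.
- **Pre-unblinding documentation of exclusions** limits discretion. It does not remove selection by completion, which is already a fixed criterion.

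**Conclusion.** The point holds in a limited form. The protocol lets equivalence be concluded from completers without major violations, requires no agreement with a fuller set, and defines its FAS by treatment duration after randomisation. An analysis plan can add an FAS analysis, but it would inherit that definition unless the protocol is amended.

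The consequence depends on the PP result. Near a PP difference of 0 the conclusion is robust, since the excluded would have to differ by about 1.48 g/dl. At an observed 0.2 g/dl, which passes in PP, about 0.68 g/dl is enough. These thresholds assume 20% excluded equally in each arm, SD 1.1 g/dl in both sets, and outcomes known for all 158 per group. They show how far the PP result could be from the randomised comparison. They do not predict that it will be. The illustration covers hemoglobin only, but the same patients also leave the weekly-dose endpoint.

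**What to change.** 1. **Section 10.6.2.2:** delete the condition of more than 4 weeks of treatment. The FAS becomes all randomised, treated patients with at least one post-baseline value, analysed as randomised.
2. **Sections 10.6.1 and 10.6.4.1:** keep PP as primary. Run the same two one-sided tests and ANCOVA for hemoglobin and weekly dose on this FAS, and make the equivalence conclusion depend on the FAS result being consistent with PP. Requiring both sets to lie within the margins is preferable. A pre-stated consistency criterion is the weaker alternative.
3. **Section 10.6.8:** state that the withdrawal rule applies to the FAS. Add a sensitivity analysis that does not rely on LOCF, for example a repeated-measures model on the biweekly hemoglobin and dose data, with its missing-at-random assumption stated.

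The cost is protocol wording, a second run of the planned model and one sensitivity analysis. The chance of success falls slightly: FAS hemoglobin power is at most 98.3% at SD 1.1 and 92.4% at SD 1.3. The sample size stays at 316. The change does not recover evaluation-period outcomes that were never observed, so the FAS result will still rest on a missing-data assumption.
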